## **12.0 Withdrawal of Participants**

*12.1* Withdrawal Circumstances:

Patients can withdraw at any time.

Patient can be withdrawn without consent by the PI and key personnel for unexpected adverse events (AEs) or unanticipated problem (UAPs) that could be study related. This would be discussed with [name] MD, director of heart failure, and reported to the IRB within 48h.

*12.2* Withdrawal Procedures:

No continued data collection after withdrawal

*12.3* Termination Procedures:

The data will be used for AE and UAP reporting to the IRB and in a publication

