#### **Cilostazol 100mg BID (white) versus Placebo BID (colored or different shape – to confirm adherence)**

The cilostazol and placebo pills are in a preloaded pill-organizer box (see below).

- study start at first day of the month (to facilitate adherence)
- two in person study visits on **day 5-7** and **day 25-28** for blood draw **and vital signs**
- four scheduled phone calls (days: **7, 14, 21 and 28**) : heart failure questionnaires

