## **13.0 Risks to Participants**

*13.1* Foreseeable Risks:

Headaches 34% (+20% over placebo)

Palpitations 10% (+9% over placebo)

Diarrhea 19% (+12% over placebo)

Additional Risks:

left ventricular outflow tract obstruction, any type of heart failure, bleeding

dyscrasias, blood dyscrasias and drug interactions.

*13.2* Reproduction Risks:

minimal, HFpEF is a disease outside the typical reproductive ages

*13.3* Risks to Others:

N/A

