## **18.0 Provisions to Monitor the Data to Ensure the Safety of Participants**

*18.1* Data Integrity Monitoring. Describe the following:

- The PI will personally oversee the progress of the study and to ensure that it is conducted, recorded, and reported in accordance with the protocol, standard operating procedures, and applicable regulatory requirements. Maintenance of, and the assurance of, data accuracy and consistency over its entire life-cycle will be monitored by the principle investigator and [name]. NTproBNP and heart failure scores data integrity will be assessed and verified by both investigators.
- CTSI monitoring service will be utilized to provide regular monitoring visits every 6 month or if there is any concern that data integrity is compromised to assure that the study is conducted, recorded, and reported in compliance with Good Clinical Practice. Monitoring is provided at no cost to PIs.

*18.2* Data Safety Monitoring.

There is no formal DSMB. AEs and UOPs will be reported to the clinical director of heart failure [name] MD. If she recommends a change in protocol this will be directly communicated to the IRB and enrollment will be halted until the changes are approved.

The data will be continuously monitored by the PI and shared in a de-identified file amongst key personnel.

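### Sections 12.1, 12.3, 13.1 and 18.2 differ in which adverse events they cover, and no described study contact asks about side effects

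*Combined protocol and SAP*

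**What the plan says.** Section 12.1 opens with the patient's own right: "Patients can withdraw at any time". It then gives the investigators' ground: "Patient can be withdrawn without consent by the PI and key personnel for unexpected adverse events (AEs) or unanticipated problem (UAPs", limited to events "that could be study related". The next sentence says this would be discussed with the director of heart failure and "reported to the IRB within 48h". Section 12.3 mentions AE and unanticipated-problem reporting to the IRB, with no limit to unexpected events and no deadline.

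Section 13.1 lists foreseeable risks with rates, for example "Headaches 34% (+20% over placebo"), and then additional risks: "left ventricular outflow tract obstruction, any type of heart failure, bleeding". The line breaks there; the item is bleeding dyscrasias, followed by blood dyscrasias and drug interactions. Section 4.2 gives the same list, taken from the package insert.

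Section 18.2 says there is no formal DSMB and that "AEs and UOPs will be reported to the clinical director of heart failure". It sets no deadline and mentions the IRB only for a recommended protocol change.

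Section 4.1 schedules "four scheduled phone calls (days" 7, 14, 21 and 28) for heart failure questionnaires, and two visits for a blood draw and vital signs. Section 5.2 names the questionnaire as the KCCQ-12, administered by the PI by telephone.

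**The concern.** Staff faced with an event on treatment need to know which provision covers it. The one stated ground for investigator withdrawal, and the one stated IRB deadline, depend on a word that the protocol never defines. The protocol also names in advance several harms to which that word might or might not apply. Heart failure is the clearest case, because every participant already has HFpEF. With no DSMB, and with external monitoring visits every 6 months (18.1) against one month of participation (5.3), the wording of these sections carries much of the safety oversight.

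The second matter is ascertainment. A placebo-controlled crossover in which each patient serves as their own control is well placed to compare side effects between drug and placebo weeks, but only if they are asked about in the same way in each week. Spontaneous reporting may be uneven. Under 12.2 data collection also stops at withdrawal, so a patient who leaves because of a side effect contributes nothing afterwards.

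**Working it through.** The plan gives no figure to reproduce. The check sets the passages side by side.

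**Scope of each provision**

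| Section | Events covered | Route | IRB deadline | Investigator withdrawal ground |
|---|---|---|---|---|
| 12.1 | Unexpected AEs or unanticipated problems, possibly study related | Director of heart failure, IRB | 48 hours | Yes |
| 12.3 | AEs and unanticipated problems | IRB | None stated | None stated |
| 18.2 | AEs and 'UOPs' (not defined) | Clinical director; IRB if a protocol change is recommended | None stated | None stated |

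**Test case: heart failure worsens in a cilostazol week.**

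1. Sections 4.2 and 13.1 name heart failure as a risk.
2. If a risk named in advance counts as expected, the event falls outside 12.1. It still goes to the clinical director under 18.2 and comes within the AE reporting mentioned in 12.3, in both cases with no time limit.
3. If unusual severity or frequency can make a listed event unexpected, it falls inside 12.1 and the 48 hours apply.
4. The text does not choose between steps 2 and 3. It also leaves open whether the 48-hour report concerns the event or the withdrawal.

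**Scheduled contacts.** Weekly periods are taken from 15.3, which uses the score at the end of weeks 1 to 4.

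| Week | Visit (blood draw, vital signs) | Call (KCCQ-12) |
|---|---|---|
| 1 | Day 5-7 | Day 7 |
| 2 | None | Day 14 |
| 3 | None | Day 21 |
| 4 | Day 25-28 | Day 28 |

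No contact is described as asking about headache, diarrhoea, palpitations or the other effects in 13.1. With alternating weeks, cilostazol is taken in weeks 1 and 3 or in weeks 2 and 4. In either order one cilostazol week (3 or 2) has no visit. Every week ends with a call.

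**Scale, for illustration.** The cilostazol rates are from 13.1; each placebo rate is that rate minus the stated excess. N = 25 is from 10.1.

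- Headache: 25 × 0.34 = 8.5; placebo 25 × (0.34 − 0.20) = 3.5
- Diarrhoea: 25 × 0.19 = 4.75; placebo 25 × (0.19 − 0.12) = 1.75
- Palpitations: 25 × 0.10 = 2.5; placebo 25 × (0.10 − 0.09) = 0.25

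With the 18 completers of 15.2, the cilostazol counts are 18 × 0.34 = 6.1, 18 × 0.19 = 3.4 and 18 × 0.10 = 1.8. Section 13.1 gives no exposure time for its rates, so these are not forecasts for one-week periods. It gives no rate for heart failure or the dyscrasias, so no count is offered for them.

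**The case against.** The case on the other side is substantial. Section 12.1 is permissive: it states a ground for withdrawal without consent and does not say that it is the sole ground. Patients may leave whenever they wish, so the gap bites mainly when a patient does not want to stop. Sections 12.1, 12.3 and 18.2 can all be followed together. All of this stands.

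A reader might therefore infer too much in four ways. The documents do not show that an investigator is barred from withdrawing a patient for a foreseen harm. They do not show that foreseen harms go unreported, because 12.3 and 18.2 cover AEs without an expectedness limit. They do not show that a listed event stays outside 12.1 however severe it is, because the key word is undefined. And they do not name bleeding events as such: the listed item is bleeding dyscrasias, a condition, and it is also an entry exclusion in section 8.0.

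On ascertainment, no passage says that the calls are restricted to the questionnaire. The PI makes each call, and a weekly heart failure questionnaire may well register worsening heart failure. Section 9.2 promises close monitoring and 18.2 continuous review of the data by the PI. The flow figure and the consent document were not available for this check. It would also go too far to say that side effects cannot be assigned to a treatment, since a dated report can be placed in a week. What remains is that no described procedure asks for them or records their onset. Tolerability is not a listed outcome, so this is an improvement to safety recording and not a flaw in the primary analysis.

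**Conclusion.** The point holds in a limited form. Sections 12.1, 12.3, 13.1 and 18.2 differ in scope without strict contradiction, and they leave undefined the term that decides whether the withdrawal ground and the 48-hour report apply. With no DSMB, they should be reconciled. Separately, none of the six described contacts (four calls and two visits) asks about the effects in 13.1, so side effects by treatment period rest on spontaneous report.

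Neither part can be sized from the documents. The counts above show only that listed side effects are common enough to be worth recording; they do not show how often a withdrawal or an urgent report would be needed. The second part assumes weekly treatment periods and that the text of 4.1 and 5.2 describes the contacts in full. An adverse-event question in the flow figure or call script would remove it.

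**What to change.** The sponsor and the clinical director should reconcile 12.1, 12.3, 13.1 and 18.2: define when an event is unexpected, state which events each provision covers, and say whether the 48 hours run for the event or for the withdrawal. Which withdrawal or reporting rule to adopt is for them, and none is proposed here. The cost is rewording.

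In 4.1 and 5.2, add a short fixed adverse-event question to each of the four existing calls (days 7, 14, 21 and 28). It should include the effects named in 13.1 and record the onset date. Ask it in the same words every week, since only patients are stated to be blinded and the PI makes the calls. Put it after the KCCQ-12, so that it cannot colour the primary outcome. In section 15, add a table of events by the treatment of the period. The cost is a few minutes per call and somewhat more events to record; no new contact is needed.

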## **13.0 Risks to Participants**

*13.1* Foreseeable Risks:

Headaches 34% (+20% over placebo)

Palpitations 10% (+9% over placebo)

Diarrhea 19% (+12% over placebo)

Additional Risks:

left ventricular outflow tract obstruction, any type of heart failure, bleeding

dyscrasias, blood dyscrasias and drug interactions.

*13.2* Reproduction Risks:

minimal, HFpEF is a disease outside the typical reproductive ages

*13.3* Risks to Others:

N/A

## **14.0 Potential Benefits to Participants**

*14.1* Potential Benefits:

moderate chance (>30%) at improving heart failure symptoms within 48h after first dose of cilostazol

## **15.0 Statistical Considerations**

*15.1* Data Analysis Plan:

Primary outcomes

**KCCQ heart failure questionnaire:** paired parametric test (t-test) of placebo average composite score and the cilostazol average composite score.

**NTproBNP:** Relative changes in NTproBNP level (placebo versus cilostazol) will be compared by paired parametric testing (t-test).

*15.2* Power Analysis:

In a recent large HFpEF clinical trial of sacubitril/valsartan the baseline KCCQ score was  $71 \pm 19$ . A sample size of 18 would provide us with 80% power to detect a 25% relative difference using a 2-sided test. We propose a sample size of 25 participants to ascertain 18 or greater completed studies. In a recently completed pacemaker study that leads to a similar increase in heart rate we found a beneficial outcome in a heart failure questionnaire in n=22 participants (see reference #4, Wahlberg et al.).

*15.3* Statistical Analysis:

Linear mixed-effect models determine the effect of cilostazol on the primary outcome, accounting for inter-patient differences and treatment assignment and sequences. For the primary endpoint, the KCCQ total score at the end of each week (week 1 to 4) is the dependent variable, while the treatment (cilostazol versus placebo) is the independent variable. Patient identifier and treatment sequence (binary variable marking the start of the treatment with placebo or cilostazol) are entered as random effects. The same approach was taken to assess the effect of cilostazol on NT-proBNP levels, after log-transforming NT-proBNP values given their skewed distribution. To determine the

treatment effect paired analyses of subsequent treatment periods will be performed (Wilcoxon test) to match weeks and the days within the treatment period.

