### *1.2 Primary outcome:*

1. standardized heart failure questionnaire  
(sample provided at the end of the consent document)

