### *2.2 Preliminary Data:*

Cilostazol is approved for the use in peripheral artery disease and has been used in patients with diastolic dysfunction-induced atrial fibrillation and HFpEF. This results in a symptomatic relief and significant reductions in the heart failure blood marker BNP (7,8). In our own clinical experience, cilostazol reduces HFpEF symptoms and lowers NTproBNP by about 25% to suggest a clinical benefit that is in line with the cilostazol-induced changes in BNP in patients with atrial fibrillation (7,8). No adverse effects were noted in our own HFpEF patients that chronically take cilostazol.

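### Section 15.1 tests NTproBNP by relative change with no stated denominator, 15.3 models the same values on logs, neither is given precedence, and 15.1 heads NTproBNP as primary

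*Combined protocol and SAP*

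**What the plan says.** Section 15.1 gives this test for NTproBNP: "Relative changes in NTproBNP level (placebo versus cilostazol) will be compared by paired parametric testing (t-test"). It supplies no formula, and the bracketed words name the contrast without naming a denominator. Section 15.3 then says: "The same approach was taken to assess the effect of cilostazol on NT-proBNP levels, after log-transforming NT-proBNP values given their skewed distribution". The approach it refers to is the one introduced by "Linear mixed-effect models determine the effect of cilostazol on the primary outcome". No section ranks these two NTproBNP analyses or labels either a sensitivity analysis.

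Section 5.2 schedules two NTproBNP draws, one on each treatment (days 5 to 7 and days 25 to 28). It lists no pre-treatment study draw that could serve as a denominator.

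On outcome rank, 1.2 names only the "standardized heart failure questionnaire" as primary and 1.3 makes NTproBNP secondary. Section 15.3 ties the primary endpoint to KCCQ. Section 15.1 nevertheless puts both measures under a plural primary-outcomes heading.

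For KCCQ, 15.1 sets a "paired parametric test (t-test) of placebo average composite score and the cilostazol average composite score", 15.3 sets the mixed model, and 15.3 ends with "paired analyses of subsequent treatment periods will be performed (Wilcoxon test) to match weeks and the days within the treatment period", without naming the outcome.

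**The concern.** Percent change and log ratio are different test statistics on the same two numbers, and they can reach different conclusions. Percent change also depends on which value is the denominator, and its mean is off zero when treatment does nothing. Section 15.3 gives skewness as its reason for taking logs, yet 15.1 does not carry that reason over. As written, the scale, the denominator and the test could all be chosen after the data are seen. The 15.1 heading adds doubt about whether NTproBNP counts as a primary result.

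**Working it through.** **The plan's own figure.** Section 15.2 states: "A sample size of 18 would provide us with 80% power to detect a 25% relative difference using a 2-sided test". With a difference of 0.25 × 71 = 17.75, SD 19 and an assumed 5% level, n = 2 × (1.960 + 0.842)² × 19² / 17.75² = 17.99, which rounds to 18. This reproduces the figure, using the formula for two independent groups. It concerns KCCQ only, and the plan gives no sample size or power for NTproBNP. Here 18 serves only as the number of completers.

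**Inputs.** C and P are a patient's cilostazol and placebo values, and r is the true geometric mean ratio C/P. Section 2.2 reports that "cilostazol reduces HFpEF symptoms and lowers NTproBNP by about 25" per cent. Three inputs are assumed because the documents do not give them: log-normal values, a log-SD per draw s of 0.1 to 0.4, and a two-sided 5% level.

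**Step 1: the denominator matters.** A ratio of 0.75 is (C − P)/P = −25%, but (C − P)/C = 1 − 1/0.75 = −33%.

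**Step 2: centre under no effect.** ln(C/P) has variance 2s², so the mean of (C − P)/P is r·exp(s²) − 1. With r = 1 this is exp(s²) − 1. By symmetry, (P − C)/C has the same mean. The direction does not need log-normality: if C and P are exchangeable, C/P and P/C share one mean, and (C/P + P/C)/2 is at least 1. The log ratio is centred at zero.

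**Step 3: error with no effect** (18 completers, 200,000 simulated trials per case).

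| s | Mean change | False harm, placebo denominator | False benefit, placebo denominator | False benefit, cilostazol denominator | Total, either denominator | Total, logs |
|---|---|---|---|---|---|---|
| 0.1 | +1% | 3.6% | 1.8% | 3.6% | about 5.4% | 5.0% |
| 0.2 | +4% | 5.0% | 1.2% | 5.1% | about 6.2% | 5.1% |
| 0.3 | +9% | 6.8% | 0.8% | 6.8% | about 7.6% | 5.0% |
| 0.4 | +17% | 8.9% | 0.6% | 8.8% | about 9.5% | 5.0% |

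If all 25 complete, the total on the placebo denominator is 5.6%, 7.4%, 10.6% and 14.3%. More data make it worse, because the offset stays while the standard error shrinks.

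**Step 4: power for r = 0.75** (18 completers).

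| s | Placebo denominator | Logs | Cilostazol denominator | Logs show benefit, placebo denominator does not |
|---|---|---|---|---|
| 0.1 | 100% | 100% | 100% | 0% |
| 0.2 | 94% | 98% | 99% | 4% |
| 0.3 | 54% | 77% | 90% | 23% |
| 0.4 | 25% | 53% | 75% | 28% |

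The reverse disagreement was practically absent. As a check on the log column at s = 0.3, the SE is 0.3 × √2 / √18 = 0.100 and ln 0.75 = −0.288. The noncentrality is therefore about 2.88, for which the t-test has 77% power. The higher power on the cilostazol denominator comes with its 6.8% false-benefit rate.

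**Step 5: what 25% means.** If section 2.2 means an average relative change from placebo, then r·exp(s²) − 1 = −0.25. At s = 0.3, r = 0.75/exp(0.09) = 0.685. Power is then about 81% (placebo denominator) against 95% (logs).

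**Step 6: incomplete pairs.** Section 15.2 enrols 25 to obtain 18 completers, the draws are about three weeks apart, and 12.2 stops data collection at withdrawal. A paired t-test drops a patient with one draw; a mixed model keeps that patient. With complete pairs, a random-intercept log model and the paired t-test on logs agreed to five decimals. With 25 patients, 7 lacking the second draw (assumed s = 0.3, between-patient log-SD 0.8), the estimates and standard errors differed in all eight simulated data sets. In one, the two log-scale estimates were −0.236 (SE 0.121) and −0.205 (SE 0.125).

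**Step 7: KCCQ, for scale.** With no effect, 18 completers, independent normal errors and no time trend, the t-test or the mixed model is positive in 6.3% of trials. This becomes 7.1% if the Wilcoxon test is also meant for KCCQ.

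**The case against.** The strongest reply is that a difference of logs is itself a relative change. On that view 15.1 is the outline (paired, relative) and 15.3 the operating detail (log scale, because of skewness). This reading is possible, so a reader who infers a flat contradiction goes too far. But the plan does not state the reading, and a t-test on percent change is an equally natural one. The size figures apply only if percent change is meant.

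It is also fair that a t-test on percent change does test something: whether the mean percent change is zero. That is not the hypothesis of no effect, as step 2 shows, and 15.3 already accepts that the raw scale is unsuitable.

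Some stronger inferences are tempting and are not supported:

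- **The fault favours the drug.** It does so only on the cilostazol denominator. On the placebo denominator, false benefit falls below 2.5%.
- **54% is the power for the effect the sponsor expects.** That needs the 25% to be a geometric mean ratio, and s to be 0.3; the documents establish neither.
- **NTproBNP is a co-primary outcome.** Only the 15.1 heading suggests this; 1.2, 1.3 and 15.3 point the other way.
- **The paired t-test on logs and the 15.3 model are interchangeable.** They are not once pairs are incomplete, which the plan expects.

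Finally, section 4.1 calls the study exploratory, and NTproBNP is secondary. That limits the consequences, but does not remove the value of fixing the test in advance.

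**Conclusion.** The concern stands as an unresolved choice of NTproBNP analysis, with a mislabelled heading, and should be fixed before analysis. It is not fatal, because 15.3 already contains a suitable log-scale analysis.

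The ambiguity is in the text and needs no assumption. Its size depends on reading relative change as percent change, on a two-sided 5% level, on log-normal values and on s, for which the documents give nothing. It runs from negligible at s = 0.1 to a near doubling of total error at s = 0.4. The loss of power on the placebo denominator is substantial at s = 0.3 and above.

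The unranked KCCQ tests and the Wilcoxon sentence are minor. A reader might infer serious inflation of the primary error rate, but step 7 puts it at one to two percentage points.

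**What to change.** 1. In 15.1, delete the relative-change t-test. Name the 15.3 mixed model on log values as the NTproBNP analysis, keeping patients who have only one draw. Report the cilostazol/placebo geometric mean ratio with its 95% confidence interval. Label a paired t-test on ln(cilostazol) minus ln(placebo) in complete pairs a sensitivity analysis, and do not describe the two as the same analysis.
2. In 15.1, list KCCQ as primary and NTproBNP as secondary, matching 1.2 and 1.3.
3. Minor: before analysis, name either the 15.1 t-test or the 15.3 model as the primary KCCQ test, at the sponsor's choice. Label the other a sensitivity analysis. State which outcome the Wilcoxon test serves and label it a sensitivity analysis too.

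The cost is wording only, with no added patients, visits or samples. The sponsor gives up choosing the denominator or the test after seeing the data.

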## **1.0 Objectives**

### *1.1 Purpose:*

Determine if cilostazol improves symptoms and NTproBNP levels (heart failure blood marker) in heart failure with preserved ejection fraction (HFpEF) – a prevalent syndrome without evidence-based treatment.

This will be assessed in a prospective 1-month single blinded study with 2 cross-overs (n-of-1 study design with placebo and cilostazol)

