## 4.0 Study Intervention(s)

### 4.1 Description:

We propose a n-of-1 study design using the standard dose cilostazol formulation of 100mg twice a day approved in peripheral vascular disease. The patients will be blinded and serve as their own controls with two crossovers (cilostazol – placebo – cilostazol - placebo). This exploratory study is neither designed nor powered to seek a change in

[figure not shown]

the drug approval and thereby does not require an FDA investigational new drug (IND) application (see section 4.1). The study aims to minimize in-person visits during the ongoing COVID-19 pandemic.

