## **7.0 Sharing of Results with Participants**

- 7.1 Patient will be informed of their personal results: benefit – no benefit.  
If requested by the participant the treating provider will be contacted to discuss the potential benefits of a cilostazol prescription.
- 7.2 Sharing of genetic testing: N/A

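### The KCCQ paired t-test (15.1) and mixed model (15.3) are not ranked, and the model's standard error can be wrong in either direction because it has no patient-by-treatment term

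*Combined protocol and SAP*

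**What the plan says.** Purpose 1.1 is put in general terms: "Determine if cilostazol improves symptoms and NTproBNP levels (heart failure blood marker) in heart failure with preserved ejection fraction (HFpEF"). In section 4.1, "The patients will be blinded and serve as their own controls with two crossovers", so each treatment is given for two of the four weeks. Section 5.2 schedules the KCCQ-12 on days 7, 14, 21 and 28, and NTproBNP once near the start and once near the end of the month.

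The analysis text then offers:

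- **15.1, under primary outcomes:** "paired parametric test (t-test) of placebo average composite score and the cilostazol average composite score".
- **15.3, mixed model:** "For the primary endpoint, the KCCQ total score at the end of each week (week 1 to 4) is the dependent variable", with treatment as the independent variable. "Patient identifier and treatment sequence (binary variable marking the start of the treatment with placebo or cilostazol) are entered as random effects". No patient-by-treatment effect is named.
- **15.3, last sentence:** "treatment effect paired analyses of subsequent treatment periods will be performed (Wilcoxon test) to match weeks and the days within the treatment period". No outcome is named.

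None of these is called primary, supportive or a sensitivity analysis. Section 15.2 does not say which test its power figure is for. The plan mentions no confidence interval, so the point below concerns the model's standard error and p-value, and any interval built from them.

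**The concern.** A patient intercept absorbs differences in level between patients. It does not absorb differences in response. If cilostazol helps some patients more than others, a patient's two cilostazol-placebo contrasts share that patient's own effect and are not two independent pieces of evidence about HFpEF patients in general. The 15.3 model treats them as if they were. The 15.1 t-test does not, because it reduces each patient to one difference.

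Two analyses with different error properties therefore both have a claim to be the primary one. They can disagree for this reason alone, and the choice between them could be made after the results are seen. If the model is the one reported and response varies, the average effect will look more precise than it is.

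**Working it through.** **The plan's own figure.** From 15.2: mean 71, SD 19, 25% relative difference, 80% power, two-sided (5% level assumed). The difference is 0.25 × 71 = 17.75 points. The two-group formula gives 2 × (1.960 + 0.842)² × 19² / 17.75² = 17.99, so 18. This reproduces the stated number, but as 18 per group for two independent groups. The SD of 19 is a baseline SD between patients. It says nothing about the quantities needed here.

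**Inputs.** From the documents: 18 completers (n), four weekly scores, two per treatment, alternating. Assumed, because the documents give none of them: tau (SD between patients of the true effect), sigma (weekly residual SD) and rho (AR(1) correlation between adjacent weeks). Coverage depends only on tau/sigma and rho. Widths below use sigma = 8 points.

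**Independent weeks, by formula.** Each patient's difference (mean of two cilostazol weeks minus mean of two placebo weeks) has variance sigma² + tau².

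- True variance of the average effect: (sigma² + tau²)/n.
- Expected variance used by 15.3: the within-patient residual has 3n − 1 = 53 df, of which n − 1 = 17 carry tau². This gives (sigma² + (17/53) tau²)/n.
- Example, tau = sigma = 8: true SE = √((64 + 64)/18) = 2.67. Model SE = √((64 + 20.5)/18) = 2.17. The ratio is 0.81.

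**Correlated weeks.** With rho = r, the patient difference has variance sigma²(1 − 1.5r + r² − 0.5r³) + tau². The other two within-patient df average sigma²(1 − r²). The model's SE is right on average when these are equal, which gives tau² = sigma²(1.5r − 2r² + 0.5r³). Break-even tau is 0.47, 0.53 and 0.56 sigma at r = 0.2, 0.3 and 0.5, and never exceeds about 0.56 sigma for positive r. Below break-even the model is too conservative, above it too optimistic.

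**Simulated coverage of the population average and mean half-widths** (n = 18, sigma 8):

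| rho | tau | tau/sigma | 15.3 coverage | 15.1 coverage | Half-width, 15.3 vs 15.1 |
|---|---|---|---|---|---|
| 0 | 0 | 0 | 95.0% | 95% | 3.76 vs 3.92 |
| 0 | 4 | 0.5 | 93.2% | 95% | 3.91 vs 4.38 |
| 0 | 6 | 0.75 | 91.3% | 95% | 4.09 vs 4.90 |
| 0 | 8 | 1 | 89.0% | 95% | 4.32 vs 5.54 |
| 0.3 | 0 | 0 | 97.4% | 95% | 3.41 vs 3.10 |
| 0.3 | 4 | 0.5 | 95.3% | 95% | 3.57 vs 3.67 |
| 0.3 | 6 | 0.75 | 92.8% | 95% | 3.76 vs 4.27 |
| 0.3 | 8 | 1 | 90.0% | 95% | 4.02 vs 5.00 |

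With 25 completers and independent weeks, 15.3 covers 93.2, 91.4 and 89.0% at tau 4, 6 and 8, so more patients do not help.

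**Where there is no shortfall.** For the average effect in the enrolled patients alone, 15.3 covers 95.0 to 97.5% with independent weeks. If no patient has any effect and weeks are independent, the test keeps its 5% level. NTproBNP has one value per treatment, hence one contrast per patient, and is unaffected. Sequence is constant within a patient; mixed-model fits with and without it gave the same coverage.

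**Wilcoxon test.** If it is a KCCQ test and each patient gives two pairs (weeks 1-2 and 3-4), then with a zero population average and independent weeks it rejects in 5.2, 6.2, 7.3 and 8.6% at tau 0, 4, 6 and 8. With one averaged difference per patient it rejects in 4.7 to 5.0%.

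**The case against.** The best defence is that the documents cannot show the fault operating, or even its direction. Tau, sigma and rho are all assumed. Positive correlation between weekly questionnaires is plausible, and at rho 0.3 with tau at half of sigma there is no shortfall. This stands, and it is why the point is conditional.

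A reader might infer that response is known to vary, because "Patient will be informed of their personal results: benefit – no benefit" and because section 14.1 promises a "moderate chance (>30%) at improving heart failure symptoms within 48h after first dose of cilostazol". Neither supports that. Both fit a constant effect seen through weekly noise just as well.

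The target is also open to argument. The study is called exploratory and n-of-1, recruits from one institution's cardiology service and names no estimand. For the enrolled-patient average, the random-intercept model is defensible. The general wording of 1.1 favours the population reading without compelling it, so the plan should say which it means.

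A reader might also count three KCCQ analyses as fact. The Wilcoxon sentence names no outcome and follows the NT-proBNP sentence. KCCQ is the likelier reading, since only KCCQ is measured in all four periods, but that is an inference. The layout of two pairs per patient is a further assumption.

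Finally, the sound analysis is already in the plan, under primary outcomes. That is true, but 15.3 also claims the primary endpoint, so the text does not settle the matter.

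**Conclusion.** What the documents show is that the t-test and the mixed model are unranked and have different error properties. The missing patient-by-treatment term is a conditional reason to prefer the t-test. For the average effect in HFpEF patients, the 15.3 standard error is too small once tau passes a break-even that depends on rho (zero with independent weeks, at most about 0.56 sigma with positive AR(1) correlation). It is too large when the effect is constant and weeks are positively correlated. Over the assumed values tabulated, its coverage runs from 89.0 to 97.4%, against 95% for the paired t-test. The loss is under 2 percentage points up to tau = 0.5 sigma and becomes material from about 0.75 sigma.

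The stronger reading, that the planned model will overstate precision in this trial, is not supported: no document gives tau, sigma or rho. This is a cheap improvement to make before analysis, not a demonstrated error in the result.

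**What to change.** State that the target is the average effect in HFpEF patients. Name the 15.1 paired t-test on per-patient average KCCQ scores, with its 95% interval, as the primary KCCQ analysis, and make the 15.3 model supportive. State the outcome of the Wilcoxon test and, if it is KCCQ, run it on one averaged difference per patient.

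An alternative is to keep 15.3 as primary and add a random patient-by-treatment effect for KCCQ with Kenward-Roger or Satterthwaite df. With complete data this gives the paired-t standard error whenever the added variance is estimated above zero, and otherwise falls back to the current one. Its coverage was 95.1 to 98.3% in the settings tested. The t-test is simpler and holds 95% in all of them.

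The change is wording only. The price is precision when the current model happens to be right:

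- **Completers only, tau 0, independent weeks:** the interval is about 4% wider (3.92/3.76).
- **Dropouts:** section 15.2 allows for 7 of 25 not completing. If those 7 give weeks 1-2 only (an assumption), at tau 0 with independent weeks the paired interval is about 7% wider than 15.3 on all the data, or about 14% wider if restricted to completers.
- **Constant effect, rho 0.3:** the paired interval is about 9% narrower (3.10/3.41).
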